9.1 Study design

This study has a cohort design.

Cohorts of first-time users of either rivaroxaban or standard of care will be identified using the date of first dispensing (index date) of the respective drug (index drug).

A patient will be considered eligible to enter the study cohort as a first-time user of rivaroxaban or a first-time user of “standard of care” when he or she has a first dispensing of the drug recorded during the enrolment period. In the Netherlands, for VTE prevention, DVT/PE treatment and SPAF, standard of care is treatment with a vitamin K antagonist (acenocoumarol or phenprocoumon), and for the secondary prevention of ACS, standard of care is antiplatelet drug(s) such as low-dose acetylsalicylic acid, clopidogrel, dipyridamole, prasugrel, ticlopidine and ticagrelor.

Patients who qualify as members of both cohorts on the same day, will be excluded. First-time users who have any record of being prescribed the other study drug prior to the enrolment period can only join their index drug cohort; these will be categorized as non-naïve, see below (i.e. patients with a previous dispensing of rivaroxaban can only join the standard of care cohort and those with a past dispensing for standard of care can only join the rivaroxaban cohort).

Patients who are first-time users of both rivaroxaban and comparison study drugs during the enrolment period will be assigned to a cohort based on first dispensing, with the date of this dispensing being the index date.

Many patients with ACS have a history of ischaemic heart disease for which platelet inhibition is standard treatment, and thus exclusion of patients with prior use of platelet inhibitors risks excluding a majority of typical ACS patients. Therefore, in patients treated for ACS, those who have been using a vitamin K antagonist or another oral anticoagulant-before the index date will be excluded but those who have been using one or more platelet inhibitors will remain eligible to enter the study.

Standard of care for ACS patients is combination therapy, and as such cohort assignment will be based on first use of rivaroxaban (in combination with aspirin or clopidogrel, or multi-antiplatelet therapy), or use of aspirin and clopidogrel and/or other antiplatelet medications.

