Study subjects for DVT/PE treatment and SPAF will be categorized as naïve or non-naïve patients according to their previous use of any comparator drugs (Figure 1). Naïve patients will be those without a previous dispensing of the comparator drug recorded before the index date. Non-naïve patients will be those with one or more dispensing of the comparator drug recorded before the index date. Non-naïve patients will be further subdivided into recent switchers (patients exposed to the other study drug in the 6 months prior to the index date) and distant switchers (patients exposed to the other study drug more than 6 months prior to the index date).

[figure not shown]

Figure 1. Subdivision of study cohorts for DVT/PE treatment and SPAF.

Data collected for comparison of cohorts is described in [Section 9.3](#)

Strengths of the study pertaining to the research question include:

- It uses observational data from routine clinical practice with no selection and no possibility to influence prescribing behaviour.
- PHARMO is a well-validated resource for pharmacoepidemiology research (see [Section 9.2](#)).

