9.2 Setting

Study drug users will be selected from the outpatient pharmacy database. This database records all outpatient dispensings from primary and secondary care in a well-defined geographic area. All study drug users living in this area will be captured in the database. All patients aged 2 years and above who have been registered in the database for at least 1 year before the index date will be included. A sub-population will be defined of patients for whom GP recorded information is also available.

The enrolment period will start on December 10, 2011 (the day after rivaroxaban received first marketing authorization in the Netherlands for the ‘treatment of DVT and long-term secondary prevention of recurrent DVT and PE’). End of enrolment will be 31 December 2017 and end of follow-up will be 31 December 2018. Interim reports will be provided for data collected 2 and 4 years after the date that rivaroxaban receives reimbursement approval for DVT treatment (see [Section 6](#) for detailed milestones). The characteristics of the two study cohorts in the first year and subsequent years of the enrolment period will be compared.

The drug utilization analysis ([Section 8.1.1](#)) will be performed in the sub-population captured by both the outpatient pharmacy database and the GP database, in order to enrich the data for the assignment of indication of use.

The Adverse Outcomes analysis (Sections [8.1.2](#) and [8.2](#)) will be performed in the full rivaroxaban cohort (outpatient pharmacy database with outcomes available from Medical Register), using the dosing as a proxy for the indication when this information is not available, and in the subcohort of comparator drug users captured by both the outpatient pharmacy database and the GP database.

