9.4 Data sources

Data for the study will be obtained from a linked cohort created using the PHARMO Database Network. The PHARMO Database Network is a population-based network of healthcare databases and combines data from different healthcare settings in the Netherlands. These different data sources are linked on a patient level through validated algorithms. Detailed information on the methodology and the validation of the used record-linkage method can be found elsewhere ([van Herk-Sukel et al. 2010](#); [Herings RMC 2012](#))

The longitudinal nature of the PHARMO Database Network system enables follow-up of more than 4 million residents (25% of total population) of a well-defined population in the Netherlands for an average of ten years. Data collection period, catchment area and overlap between data sources differs. Therefore, the final cohort size for any study will depend on the data sources included. As data sources are linked on an annual basis, the average lag time of the data is 1 year. All electronic patient records in the PHARMO Database Network include information on age, sex, socio-economic status and mortality. Other information available is dependent on the data source

To address the objectives of the present study, the following data sources will be used: outpatient pharmacy database, Dutch National Medical Register, general practitioner (GP) data and inpatient pharmacy database. The outpatient pharmacy database has a source population of about 4 million residents and is fully linked to the national Dutch National Medical Register. The GP and inpatient pharmacy databases each represent different, partially overlapping subsets of the outpatient pharmacy/Medical Register source population.

The drug utilization analysis will be performed in the subpopulation captured by both the outpatient pharmacy database and the GP database, in order to enrich the data for the assignment of indication of use. The Adverse Outcomes analysis will be performed in the full rivaroxaban cohort (outpatient pharmacy database with outcomes available from Medical Register), using the dosing regimen as a proxy for the indication when this information is not available, and in the subcohort of comparator drug users captured by both the outpatient pharmacy database and the GP database.

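### First-time status and the split between naïve patients and distant switchers rest on open-ended recorded history, but only one year of registration is guaranteed

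*Protocol*

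**What the plan says.** **Guaranteed history.** Protocol Section 9.2 admits patients aged 2 years or over who have been "registered in the database for at least 1 year before the index date will be included". No other look-back is required.

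**First-time use and cohort assignment.** Under Section 9.1 a patient enters "when he or she has a first dispensing of the drug recorded during the enrolment period". First-time users with "any record of being prescribed the other study drug prior to the enrolment period" may join only the cohort of their index drug and count as non-naïve. Patients who start both drugs during enrolment "will be assigned to a cohort based on first dispensing, with the date of this dispensing being the index date".

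**Naïve and switcher status (DVT/PE treatment and SPAF).** Section 9.1: "Naïve patients will be those without a previous dispensing of the comparator drug recorded before the index date". Non-naïve patients are recent switchers if exposed to the other drug within 6 months before index, and distant switchers if exposed earlier than that, without an outer limit.

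**Calendar.** Section 9.2: "The enrolment period will start on December 10, 2011" and "End of enrolment will be 31 December 2017 and end of follow-up will be 31 December 2018".

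**Records.** Section 9.4 gives follow-up averaging ten years, but also warns: "Data collection period, catchment area and overlap between data sources differs".

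**The concern.** The rules ask about any recorded use, and what is recorded depends on when a patient joined the database. Three invented histories show the effect; all three patients have more than one year of registration.

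- Vitamin K antagonist (VKA) in 2010, rivaroxaban in 2016. With a full record the patient is a distant switcher in the rivaroxaban cohort. If registered from 2014, the patient is naïve.
- First VKA in 2012, rivaroxaban in 2016. With a full record the patient belongs to the VKA cohort with a 2012 index date. If registered from 2014, the patient is a naïve rivaroxaban user with a 2016 index date.
- VKA in 2010, restarted in 2014. With a full record the patient is not a first-time VKA user. If registered from 2012, the patient is.

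Two kinds of result are exposed. The proportions of naïve patients and distant switchers are listed descriptive results (Section 9.3.1) and stratify the odds ratios (Section 9.7.1). Time trends are a primary objective (Section 8.1.1), and Section 9.2 compares the first enrolment year with later years, so a change in record length can look like a change in prescribing. In the outcome analysis, unseen earlier use can change who enters a cohort, which cohort they enter and their index date.

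**Working it through.** The protocol gives no figure on look-back coverage, so there is none to reproduce. Its one calculated figure, the study size in Section 9.5, does not bear on this point.

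**1. What each rule needs, against the guaranteed year**

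| Status | History the rule uses | Covered by 1 year? |
|---|---|---|
| Recent switcher | 6 months before index | Yes, always |
| Distant switcher | beyond 6 months, open-ended | Months 6 to 12 only |
| Naïve | all time before index | First year back only |
| First-time use of the index drug | all recorded time before index | First year back only |
| Cohort by first dispensing in enrolment | back to 10 December 2011 | Only for index dates in about the first enrolment year |

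**2. How much of enrolment the last row concerns**

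- 10 December 2011 to 31 December 2017, inclusive: 2,214 days (2,214 / 365.25 = 6.06 years).
- Index dates whose guaranteed year starts on or after 10 December 2011, that is, from 10 December 2012: 1,848 days.
- 1,848 / 2,214 = 83%.
- At the last index date the guaranteed year starts about 31 December 2016. The enrolment time before it that need not be visible is 1,848 / 365.25 = 5.06 years, plus everything before enrolment.

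The 83% is a share of calendar days and matches the share of patients only under flat uptake. Under an assumed linear rise in uptake the share of patients would be 1 − (1/6.06)² = 97%. The naïve and distant rules are tied to the index date, so they depend on record length throughout enrolment, including its first year.

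**3. How sensitive the naïve share could be (illustration)**

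The protocol gives no share of past VKA users. Assume that 20% of rivaroxaban starters used a VKA in the past ten years and that all patients have the same history of h years. The effect of the assignment rule on who remains in the rivaroxaban cohort is ignored.

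- A: last VKA use spread evenly over 10 years. Observed naïve share = 1 − 0.20 × h/10.
- B: half of the past users switched within 6 months, the rest spread evenly over the remaining 9.5 years. Observed naïve share = 1 − [0.10 + 0.10 × (h − 0.5)/9.5].

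| History h | A | B |
|---|---|---|
| 1 year | 98% | 89.5% |
| 3 years | 94% | 87.4% |
| 5 years | 90% | 85.3% |
| 10 years | 80% | 80% |

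The true share is 80% in every row. If typical history lengthened from 3 to 5 years during enrolment, the naïve share would fall by 4 points under A and about 2 under B with no change in prescribing.

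**4. Whether anything in the plan deals with it**

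Section 9.7.2 adjusts for age and sex and, where possible, for co-medication, indication and earlier bleeding admission. Section 9.7.2.2 varies the start and stop of treatment and promises in general terms to account for unexpected biases. Section 9.9 does not list the issue. None of them mentions look-back length. By contrast, Section 9.3.1 gives fixed one-year windows before index for co-medication, bleeding admissions and healthcare use.

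**The case against.** **One year is a minimum, not the typical history.** This stands. With follow-up averaging ten years, many patients will have far more, and the ten-year row above shows no error. But that average describes total follow-up, not time before index, and is not an entry criterion. It limits the problem without removing it.

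**Using all available history is a recognised choice, and look-back detail belongs in a statistical analysis plan.** Partly right. All-available history identifies the most prior users and is defensible for building the main cohort. But the protocol itself fixes these definitions, and for a proportion compared across years an unequal look-back is a weakness of the definition.

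**Naïve/distant mislabelling does not change the rate ratios.** This stands for mislabelling within a cohort, because Section 9.7.2 compares whole cohorts. Only unseen use that alters entry, assignment or index date could matter there.

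**A reader might infer that the error is one-sided and lowers the VKA bleeding rate**, because the VKA cohort would hold restarters who had tolerated the drug while rivaroxaban was newly authorised for treatment. The document does not support this. VKA-experienced patients also enter the rivaroxaban cohort, openly as non-naïve or unseen as naïve. Section 9.1 itself provides for rivaroxaban use before enrolment, and later in enrolment a rivaroxaban restarter with a short record would also pass as first-time.

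**Conclusion.** The point holds in a limited form. First-time status and the naïve/distant split depend partly on how long a patient has been registered, and no planned adjustment, sensitivity analysis or stated limitation addresses it. Recent-switcher status is sound.

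The firm figure is that on 83% of enrolment days the guaranteed year no longer reaches back to the start of enrolment. A reader might take this to mean that 83% of patients are misclassified. It does not: it counts days and concerns the minimum history only. The number misclassified cannot be derived from the protocol. In the illustration, the error in the naïve share runs from zero at ten years of history to 9.5 or 18 percentage points at one year, and it rests wholly on the assumed 20% and the assumed timing of past use. Any effect on the three bleeding rate ratios is possible, but its size and direction are not established.

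**What to change.** 1. **Proportions and trend.** Report the naïve and distant-switcher proportions, and their comparison across enrolment years, with one common fixed look-back before the index date, in patients registered for at least that long: for example 3 years, with 1 and 5 years as alternatives. This removes only the part of a trend that comes from record length; the rule on assignment by first dispensing still applies.
2. **Rate ratios.** As a named sensitivity analysis, repeat the three primary rate ratios in patients continuously registered since at least 10 December 2010. All dispensings during enrolment that determine cohort assignment are then observable, with at least one year before enrolment. Use before that date is still not guaranteed to be seen.
3. **Leave unchanged** the main cohort and the ACS rule on prior platelet inhibitors.

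The restriction in item 2 should not be used for the trend. Look-back in that subset grows from 1 year at the start of enrolment to about 7 years at its end; under assumption A, and counting only that minimum, the naïve share would drift from 98% to 1 − 0.20 × 0.7 = 86% with no real change.

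Both analyses use data already held. The cost is a smaller sample in those tables. How much smaller is not known: drug utilization is already confined to patients with both pharmacy and GP data, and Section 9.4 says that cohort size depends on the sources used.

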Number	Date	Section of study protocol	Amendment	Reason
6	Jan 2015	9.3.2.1 9.7.2 9.7.2.1	Addition to section on bleeding definition Addition to section on renal failure definition Addition of section to handle missing data	Response to PRAC review
5	Nov 2014	8.2 9.3.1 9.7.1 9.7.2.1 Annex 3	Additional variables for patient characterisation and analyses thereof; strengthened analyses of renal impairment. Table 12, ICD codes related to renal impairment added	Response to PRAC review
4	May 2014	General	Extension of study timelines. Comparator updated for acute coronary syndromes. Added secondary safety outcome: "other bleeding" Transfer to EMA protocol template. Label wording updated. Current protocol is V5.0.	PRAC request
3	Mar 2012		Inclusion of additional indication, treatment of pulmonary embolism. V4.0 of protocol.	Label expansion
2	Dec 2011		Inclusion of additional indication, acute coronary syndrome. V3.0 of protocol submitted with EU RMP V	Label expansion

			7.1	
1	Apr 2011		Inclusion of additional indication, stroke prevention in atrial fibrillation. V2.0 of protocol submitted with EU RMP V 6.1.	Label expansion

6 Milestones

Table 2: Milestones

Milestone	Planned date
Start of data collection (Marketing Authorization granted for DVT treatment)	Q1 2012
Interim report 1 2 years drug utilization data and crude incidences for primary safety outcomes	Q4 2015
Interim report 2 4 years drug utilization data and crude incidences for primary safety outcomes	Q4 2017
End of data collection	Q4 2018
Final data availability	Q4 2019
Progress reports	Annual in November 2014–19
Final report of study results with full outcomes analysis	Q4 2020
Registration in the EU PAS register	Study to be registered after PRAC approval

7 Rationale and background

Rivaroxaban, a direct Factor Xa inhibitor, is licensed for multiple indications:

- The treatment of deep vein thrombosis (DVT) or pulmonary embolism (PE), and prevention of recurrent DVT and PE in adult patients (DVT/PE treatment) (15 mg rivaroxaban twice daily [bid] for 3 weeks, then 15 mg or 20 mg once daily [od]).
- The prevention of stroke and systemic embolism in adult patients with non-valvular atrial fibrillation (stroke prevention in atrial fibrillation [SPAF]) with one or more risk factors, such as congestive heart failure, hypertension, age \geq 75 years, diabetes mellitus, prior stroke or transient ischaemic attack (20 mg rivaroxaban od).

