9.5 Study Size

All patients registered in the PHARMO outpatient pharmacy database and meeting the inclusion criteria will be included. The size of the population receiving rivaroxaban will be dependent on market uptake across the indications of interest (DVT/PE treatment, ACS and SPAF).

According to a preliminary sample size calculation, based on an incidence of haemorrhagic stroke in vitamin K antagonist-treated patients of 5 per 1000 person-years, 12,000 rivaroxaban-treated patient-years and 48,000 vitamin K antagonist-treated patient-years would be required to exclude a 50% increased risk of haemorrhagic stroke in rivaroxaban-treated patients compared with vitamin K antagonist-treated patients with a power of 80%.

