9.7.2 Safety and effectiveness outcomes

The two cohorts (of first-time users of rivaroxaban and first-time users of standard of care) will be followed up from the index date until 12 months after the end of the enrolment period for potential outcomes (safety and effectiveness). For each outcome, the first hospitalization for that outcome during the follow-up period will be identified. A separate follow-up will be performed for each of the outcomes.

For all outcomes (for DVT/PE treatment, SPAF and ACS), crude incidence rates will be estimated in both cohorts, using an as-treated approach. In this, person–time will be categorized into current, recent, past and non use. Current use will refer to person–time up to 7 days after the end of supply of the index drug, recent use will refer to person–time up to 90 days after the end of current use, past use will include all person–time contribution after the end of recent use up to 1 year after the end of current use, non-use will include all remaining time person–time contribution after past-use until end of follow-up.

Age- and sex-adjusted rate ratios with 95% CIs will be estimated for each of the three adverse outcomes comparing rivaroxaban with standard of care using Poisson regression analysis. Where numbers and data permit, adjustment will be made for relevant co-medication (described in the drug utilization section), indication and previous hospitalization for bleeding.

As a general strategy, no data imputation strategies will be applied to supplement missing data. The requirement for inclusion is complete data for critical variables such as exposure to rivaroxaban or standard of care and hospitalizations for bleedings or any other outcome event; otherwise this individual is not eligible to be a member of the study population. However, missing values may occur for potential confounder or effect modifying variables. In this case, individuals with missing values will be kept in the analysis and a separate category will be created for missing values of that variable. In sub-analyses to evaluate confounding or effect modification by variables with a large proportion of missing values, the evaluation will be considered to be conducted on the subset with complete data for the variable of interest.

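### Rivaroxaban and its comparators share one enrolment window from December 2011, but the outcome model names no adjustment for calendar time

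*Protocol*

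**What the plan says.** Section 9.2 fixes the start: "The enrolment period will start on December 10, 2011 (the day after rivaroxaban received first marketing authorization in the Netherlands for the" DVT indication). It also fixes the end: "End of enrolment will be 31 December 2017 and end of follow-up will be 31 December 2018". Section 9.1 applies the same window to rivaroxaban and to standard of care; a patient is eligible "when he or she has a first dispensing of the drug recorded during the enrolment period".

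Rivaroxaban accrual is left open. Section 9.5 says: "The size of the population receiving rivaroxaban will be dependent on market uptake across the indications of interest". Section 9.2 also treats reimbursement as an event separate from authorization: "Interim reports will be provided for data collected 2 and 4 years after the date that rivaroxaban receives reimbursement approval for DVT treatment".

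For outcomes, Section 9.7.2 specifies age- and sex-adjusted rate ratios from Poisson regression. Where numbers and data permit, "adjustment will be made for relevant co-medication (described in the drug utilization section), indication and previous hospitalization for bleeding". Calendar time appears in neither set.

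For time trends, which belong to the primary objective in 8.1.1, Section 9.2 says: "The characteristics of the two study cohorts in the first year and subsequent years of the enrolment period will be compared". Section 9.7.1 describes the populations by indication, but does not link that to this comparison.

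Section 9.4 reports that Dutch hospitals are moving from ICD-9 to ICD-10 and that the code lists will gain ICD-10 codes once most admissions use them. Section 9.3.2 identifies potential cases by ICD-9-CM discharge codes.

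**The concern.** A newly launched drug is compared with long-established ones over about six years of enrolment and a further year of follow-up. If rivaroxaban starts build up gradually while vitamin K antagonist (VKA) or antiplatelet starts run at full rate from the outset, rivaroxaban person-time sits later in the calendar. Any change over the period in the recorded bleeding rate, whether from co-treatment, admission practice or coding, is then partly read as a drug effect. None of the listed adjusters removes it.

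The coding transition makes this more than a textbook worry. Read literally, admissions already coded in ICD-10 could go unrecognised until the lists are updated. Such a change in case capture depends on calendar time and would weigh unequally on cohorts that accrue at different times.

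For the descriptive objective, a first-year versus later-years contrast not reported within indication cannot separate a changing mix of indications from changing use within one.

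**Working it through.** **1. The plan's own figure.** Section 9.5 gives 12,000 rivaroxaban and 48,000 VKA person-years, 5 events per 1000 person-years, and 80% power to exclude a rate ratio (RR) of 1.5. Two-sided 5% is my assumption, since the section does not state alpha.

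- Events = (1.960 + 0.842)² / [0.2 × 0.8 × (ln 1.5)²] = 7.849 / (0.16 × 0.1644) = 298.4, so 299.
- 299 / 0.005 = 59,800 person-years, split 1:4 into 11,960 and 47,840.

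The stated size is reproduced and is not in dispute. It implies 12,000 × 0.005 = 60 and 48,000 × 0.005 = 240 events, so SE(log RR) = √(1/60 + 1/240) = 0.144.

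**2. Gap in calendar time.** From the protocol: enrolment 10 December 2011 to 31 December 2017 (6.06 years), follow-up to 31 December 2018. Assumed, because the protocol gives no such figures: 30% per year leave treatment, and the start patterns below. Mean calendar time of person-time, in years from 10 December 2011:

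| Pattern of starts | Mean |
|---|---|
| VKA constant | 4.27 |
| VKA falling by 8% of the initial level per year | 4.08 |
| Rivaroxaban, one-year ramp then plateau | 4.47 |
| Same ramp, beginning three months late | 4.58 |
| Rivaroxaban rising linearly from day 0 | 5.00 |
| Rivaroxaban rising linearly from year 1 | 5.28 |

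**3. Shift in the rate ratio.** With drift g per year in the recorded bleeding rate, shift ≈ (1 + g)^gap.

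| Scenario | Gap (years) | g = ±5% | g = ±10% |
|---|---|---|---|
| Fast uptake, VKA constant | 0.20 | 1.010 / 0.990 | 1.019 / 0.979 |
| Fast, three months late, VKA constant | 0.30 | 1.015 / 0.985 | 1.029 / 0.969 |
| Linear from day 0, VKA constant | 0.73 | 1.036 / 0.963 | 1.072 / 0.926 |
| Linear from day 0, VKA falling | 0.92 | 1.046 / 0.954 | 1.092 / 0.908 |
| Linear from year 1, VKA falling | 1.20 | 1.060 / 0.940 | 1.122 / 0.881 |

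If the cohorts accrue in parallel, the gap is zero and so is the shift.

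**4. Effect on power, and the price of adjusting.** A cruder model spreads the 60 and 240 events over six enrolment years, with a true RR of 1. Its two steeper rows assume comparator starts falling to one sixth of their first-year level; they serve only to bound the cost.

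| Accrual | RR at +5% drift, unadjusted | Power to exclude 1.5, unadjusted | Information kept after stratifying by year | Power, stratified |
|---|---|---|---|---|
| Rivaroxaban linear, comparator flat | 1.04 | 0.72 | 96% | 0.79 |
| Rivaroxaban linear, comparator falling | 1.09 | 0.61 | 82% | 0.72 |
| As above, no rivaroxaban in year 1 | 1.10 | 0.57 | 75% | 0.68 |

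At -5% drift the first row gives RR 0.96 and power 0.88: unadjusted, the study would exclude 1.5 more often than it should.

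**The case against.** The strongest reply is that confounding by calendar time needs both unequal accrual and a secular trend in rates, and the protocol documents neither. That stands. The size is also modest: a 4-6% shift is under half of the 0.144 standard error on the log scale, against a 50% margin, and fast uptake brings it to about 1%.

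A reader might infer that rivaroxaban arrived late for each added indication, leaving early pulmonary embolism and ACS comparators with no counterpart at all. The document does not support this. It gives no authorization or reimbursement date by indication. The amendment table dates protocol versions, not licences: stroke prevention in April 2011, before enrolment; ACS in December 2011, the month enrolment starts; and "Inclusion of additional indication, treatment of pulmonary embolism" in March 2012, about three months in.

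A reader might also infer that 9.2 pools the later years across all indications. It does not say so, and 9.7.1 already describes the populations by indication. What remains is that the two are not tied together.

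It can also be said that model terms belong in a statistical analysis plan, that 9.7.2.2 allows biases recognised in the utilization analysis to be accounted for later, and that 9.4 commits to updating the code lists. A separate plan may indeed add calendar year. But 9.7.2 names its adjustment set, this bias is foreseeable rather than unexpected, and updating the lists only after most admissions have changed leaves a transition period.

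**Conclusion.** The point holds as a structural weakness: one DVT-anchored window for a launching drug and its established comparators, with a named adjustment set that omits calendar time. It does not establish that the rate ratios will be biased. Conditional on the assumed uptake and exit rate, the shift is about 1% (fast uptake) to 4-6% (slow uptake) at 5% drift per year, and about 2% to 7-12% at 10%, in either direction.

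A stronger remedy is tempting: separate enrolment start dates per indication in both arms of the main analysis. The document does not support it. DVT and pulmonary embolism form one combined indication, and where diagnosis is missing the rivaroxaban indication is inferred from dosing (9.2, 9.4), so a start specific to pulmonary embolism may not be workable. The dates are not given. Restricting to concurrent comparators would also not remove channelling of patients between drugs. Availability dates therefore belong in a sensitivity analysis.

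**What to change.** - **Section 9.7.2:** split person-time by calendar year and include calendar year in every Poisson model comparing rivaroxaban with standard of care, not only where numbers and data permit.
- **Section 9.2:** report the first-year versus subsequent-years comparison by calendar year within indication.
- **Sensitivity analysis:** restrict comparators to the period when rivaroxaban was both authorized and reimbursed for the combined indication group (DVT/PE, SPAF, ACS), and state those dates in the protocol.

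The first two changes need wording and programming on data already held. The sensitivity analysis also needs the availability dates to be obtained. The statistical cost is precision: small when accrual is similar (96% of information kept in the mildest unequal case above), larger when it differs strongly (75% in the most extreme). That larger loss arises where the unadjusted estimate is most exposed to drift.
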